7.1.2 Standard of Care Study Procedures

Clinical and Radiographic Examination: Routine clinical and radiographic examination will be completed. Diagnosis will be determined with American Association of Endodontists (AAE) criteria. Treatment plan for pulpectomy/endodontic debridement is determined as discussed and approved by the attending faculty; NYS Dental Licensed Co-Investigators, in the clinic.

CONFIDENTIAL

Access cavity Preparation, Working Length Determination, Cleaning and Shaping of the Canals, Intracanal Medication and Temporization of the tooth: After obtaining soft tissue, periradicular and pulpal anesthesia, the tooth will be isolated with a rubber dam. Endodontic access cavity will be prepared. Root canals will be initiated by #10 K files and working length will be determined by electronic apex locator. Root canals will be cleaned by rotary instruments and irrigation with 3% sodium hypochlorite through the procedure. Root canal preparation will be completed a minimum size of 25/0.4 up to 40/0.4 depending on the size of the canals. Canals will be dried out with paper points and calcium hydroxide will be placed as an intracanal medicament. The teeth will be temporized with Cavit-G. Subjects will be scheduled for the completion of the root canal treatment. Subjects will attend their second visit for the completion of the treatment. They may need to come for 3rd time depending on the complexity of the tooth, post-operative symptoms or signs of ongoing infections. Those appointments will not dictate or affect the study as the subject's participation will be completed after the second visit.

7.2 Study Schedule

7.2.1 Screening

Screening and Enrollment (Day 0)

- Prescreening
- Obtain informed consent of potential participant verified by signature on written informed consent.
- Screening of potential participants for eligibility.
- Enrollment

7.2.2 Baseline

Baseline (Day 0/Day 1)

- Verify the diagnosis and the treatment plan for the tooth.
- Verify eligibility by reviewing inclusion/exclusion criteria
- Preoperative data collection: results of routine clinical and radiographic examination, endodontic diagnosis,
- Baseline OHIP14 questionnaire

Treatment

- Administer the study intervention and dental treatment
- Collect intraoperative pain with a questionnaire to the subject after the completion of the treatment.

7.2.3 Remote Data Collection

Subjects will be asked to rate their pain intensity on an NRS, report analgesic use and numbness:

- 6 hours after treatment
- 12 hours after treatment
- 24 hours after treatment
- 48 hours after treatment
- 72 hours after treatment
- 96 hours after treatment
- 120 hours after treatment

- Day 1 – OHIP14 questionnaire

- Day 5 – OHIP14 questionnaire

7.2.4 Final Study Visit

Subjects will attend the endodontic clinic for the completion/second visit of their treatment as scheduled by the treating post graduate student under the supervision of NYS Dental Licensed Co-Investigators. This visit may be several weeks after the first treatment visit. At this routine visit, compensation will be provided

CONFIDENTIAL

by a study investigator. If remote questionnaires were completed on paper, subjects will bring these forms to this visit.

The treatment may require a third visit but for the study this will be the final visit.

7.2.5 Withdrawal/Early Termination Visit

Documentation will be completed regarding the reasons for early termination/subject withdrawal.

7.2.6 Unscheduled Visit

It is possible that subject may need to attend the endodontic clinic as an emergency again because of the continuation of the symptoms or exasperation of the symptoms like pain and swelling. If one of the study investigators is being contacted, and if it is found out necessary, an unscheduled dental visit will be scheduled for the next available time in the clinic, with the treating PG student or the subject will be seen by the treating dentist on emergency as soon as possible. Details regarding the visit will be recorded for research purposes including; symptoms, treatment performed, any medication prescribed to the subject will be obtained from the treating PG student with a questionnaire.

7.3 Concomitant Medications, Treatments, and Procedures

All concomitant prescription medications related to the study taken during study participation will be recorded on the case report forms (CRFs). For this protocol, a prescription medication is defined as a medication that can be prescribed only by a properly authorized/licensed clinician. Medications to be reported in the CRF are concomitant prescription medications, over-the-counter medications and non-prescription medications.

7.4 Prohibited Medications, Treatments, and Procedures

Subjects who use ergot-type oxytocic drugs, MAOI, tricyclic antidepressant or subjects who are planned to receive sedatives for the treatment should be excluded from the study because of drug interactions unless discussed with and approved by the investigator.

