Although adequate lip numbness is achieved, pulpal anesthesia at the same time is not always guaranteed for symptomatic teeth (17). Therefore, pulpal anesthesia will be tested with cold test, after a wait time of 10 minutes, after obtaining adequate lip numbness with (Endo-Ice, Coltene, USA) in the proposed study in an

CONFIDENTIAL

attempt to test/confirm pulpal anesthesia. This is a routine procedure for the confirmation of pulpal anesthesia. This will be done to determine the success of IANB with either Lidocaine or Bupivacaine. All other injections, if needed, apart from the IANB, will be administered with Lidocaine only in both groups.

A supplemental buccal infiltration and intraligamentary (IL) injection will be given with Lidocaine HCl 2% 1:100000 to all patients, irrespective of their grouping. This approach is a routine and highly recommended for symptomatic teeth (24, 25). The effect of pulpal anesthesia will be tested with cold test (Endo-Ice, Coltene, USA). The algorithmic chart for anesthetic administration in Fig 1. will be followed as the guideline. Additional supplemental injections will be administered as portrayed in the chart, with Lidocaine HCl 2% 1:100000 if needed in order to obtain complete pulpal anesthesia.

Subjects who need supplemental injections more than 2 times will be excluded from the study because number of injections may also contribute to postoperative pain and discomfort.

The maximum recommended dose for lidocaine is 500mg per day, and it shouldn't exceed 7mg/kg of body weight. The maximum recommended dose for bupivacaine is 400 mg per day. There are no reported risks with these doses. All these supplemental injections will be performed with Lidocaine HCl 2% 1:100000 in both groups.

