Small doses of LAs injected into the head and neck area, as small as nine to eighteen milligrams, may produce adverse reactions similar to systemic toxicity seen with unintentional intravascular injections of larger doses. Confusion, convulsions, respiratory depression, and/or respiratory arrest, cardiovascular stimulation or depression and cardiac arrest have been reported. Reactions resulting in fatalities have occurred on rare occasions. In a few cases, resuscitation has been difficult or impossible despite apparently adequate preparation and appropriate management. These reactions may be due to intra-arterial injection of the LA with retrograde flow to the cerebral circulation. Patients receiving these blocks will have their circulation and respiration monitored and be constantly observed. Resuscitative equipment and personnel for treating adverse reactions will be immediately available. Dosage recommendations should not be exceeded. It is essential that aspiration for blood be done prior to injecting any LA, both the original dose and all subsequent doses, to avoid intravascular injection. However, a negative aspiration does *not* ensure against an intravascular injection. Reactions resulting in fatality have occurred on rare occasions with the use of LAs, even in the absence of a history of hypersensitivity.

The solutions, which contains a vasoconstrictor, should be used with extreme caution for patients whose medical history and physical evaluation suggest the existence of hypertension, arteriosclerotic heart disease, cerebral vascular insufficiency, heart block, thyrotoxicosis and diabetes, etc., as well as patients receiving drugs likely to produce alterations in blood pressure. Only subjects who are ASA I and II are included in the study.

Bupivacaine with epinephrine 1:200,000 or other vasopressors should not be used concomitantly with ergot-type oxytocic drugs, because a severe persistent hypertension may occur. Likewise, solutions of

CONFIDENTIAL

This material is the property of the NYU School of Medicine and Langone Medical Center. Do not disclose or use except as authorized in writing by the study sponsor

bupivacaine containing a vasoconstrictor, such as epinephrine, should be used with extreme caution in patients receiving monoamine oxidase inhibitors (MAOI) or antidepressants of the triptyline or imipramine types, because severe prolonged hypertension may result. Subjects who use these drugs will be excluded from the study.

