5.2 Exclusion Criteria

An individual who meets any of the following criteria will be excluded from participation in this study:

1. Medically complex patients with severe systemic diseases (ASA III or above). These may include uncontrolled diabetes, uncontrolled blood pressure and/or chronic renal failure, for example, and potential participants will be asked about these conditions during the screening process.
2. Pregnant patients.
3. Patients who have already been enrolled in the study. Patients can only be enrolled for treatment on one tooth. If a patient has been enrolled in the study and will receive additional endodontic treatment on a different tooth on a later date, they will not be enrolled again for the additional endodontic treatment on a different tooth.
4. Patients with a known hypersensitivity or allergy to any local anesthetic agent of the amide group, or any other components of the two anesthetic solutions such as epinephrine, sodium metabisulfite used in the study.
5. Patients who use ergot-type oxytocic drugs for uterine contraction, monoamine oxidase inhibitors, antidepressant of triptyline or imipramine types or patients who are planned to receive sedatives for the treatment.
6. Patients with additional elective dental treatments like extraction, implant placement, root canal therapy planned in the 5 days following the date of enrollment in this study.
7. Patients with pain whose examined tooth is planned for vital pulp therapies e.g. pulpotomy, retreatment, apical surgery or extraction.
8. Patients with a pulpal diagnosis of reversible pulpitis, previously treated, previously initiated therapy and periapical diagnosis of acute apical abscess or chronic apical abscess.
9. Patients who have multiple teeth with odontogenic pain at the time of the screening.
10. Patients who do not understand or are able to read the questionnaires.
11. Non-English speaking patients.

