5.5 Strategies for Recruitment and Retention

Patients recruited in this study will be mostly those who present for emergency dental treatment at NYU Dentistry Endodontic Clinic. The dental providers are postgraduate students from the endodontic department and they work under the supervision of the NYS Dental Licensed faculty, listed as Co-Investigators, who will be overseeing the procedures and treatments which are part of the study. Study investigators (the PI, Co-PIs;) will identify patients who need an emergency treatment either by inquiring directly to the dental providers at the start of the clinic session and through the day or by asking the front desk patient representatives in the Endodontic clinic if any emergency patients presented on that day. It is also possible that some patients who come for a treatment appointment might have a symptomatic tooth.

The potential participant's standard of care clinical and radiographic examination findings, diagnosis and treatment plan approved by the faculty will be prescreened by one of the study investigators after the standard of care clinical and radiographic examinations performed by the treating dentist to determine whether the patient is eligible in terms of diagnosis and treatment plan approved by the faculty by reviewing the gathered findings. This will be done in an effort to not to increase the wait time period for patients. After prescreening, potential participant will be asked by their dental provider if they are interested in discussing participation in a research study regarding postoperative pain with a research investigator. Interested subjects will be introduced to the study – this means the purpose of the study will be explained, details of what will be involved if they decide to participate will be described, duration of the study etc. by the PI or the Co-I; [name]. If they agree to participate, they will be consented by the PI or the Co-I; [name].

Interested potential subjects will be screened for eligibility by one of the study investigators and will be enrolled if they meet all the eligibility criteria.

We estimate 80 subjects (randomized to 40 participants per arm) are required. We estimate that loss of subjects will be minimal due to a short follow up time of 1 week, however in order to anticipate a greater loss of subjects because of intraoperative exclusion criteria, we will increase our sample size to 100 to include 20% attrition (n=50 per treatment group).

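### Section 7.4 lets the investigator waive, with no stated criterion, a drug and sedation exclusion that section 5.2 makes absolute (as does section 2.4.1 for the three drug classes)

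*Combined protocol and SAP*

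**What the plan says.** Three sections of the protocol address the same patients.

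- **Section 5.2, criterion 5** excludes "Patients who use ergot-type oxytocic drugs for uterine contraction, monoamine oxidase inhibitors, antidepressant of triptyline or imipramine types", together with "patients who are planned to receive sedatives for the treatment". The sentence that introduces the list makes exclusion mandatory for anyone meeting any criterion. No exception is given.
- **Section 2.4.1** names the three drug classes, explains the hypertension hazard, and concludes: "Subjects who use these drugs will be excluded from the study". Again there is no exception. Sedatives are not mentioned there.
- **Section 7.4** covers the three drug classes and planned sedation, but says that these subjects "should be excluded from the study because of drug interactions unless discussed with and approved by the investigator".

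On enrolment, section 5.5 says that screened patients "will be enrolled if they meet all the eligibility criteria". Section 7.1.1 repeats this, and section 7.2.2 has eligibility checked against the inclusion and exclusion lists again at baseline. None of these steps mentions a waiver.

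**The concern.** Two members of staff who follow different sections could reach opposite decisions on the same patient. Section 7.4 does not say what would justify approval, which investigator gives it, how it is documented, or what additional monitoring would apply. Section 13.8 requires deviations to be reported within 7 working days, but the text does not settle whether enrolling a waived patient is a deviation.

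The matter at stake is patient safety. The protocol gives severe hypertension as its reason for excluding the three drug classes, and both study solutions contain epinephrine.

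**Working it through.** This is a comparison of text. No power, alpha or sample size figure depends on it, and the plan states no number to reproduce.

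**Step 1. The rules side by side**

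| Group | 5.2, criterion 5 | 2.4.1 | 7.4 |
|---|---|---|---|
| Ergot-type oxytocics | Excluded, no exception | Excluded, no exception | Waivable |
| MAO inhibitors | Excluded, no exception | Excluded, no exception | Waivable |
| Tricyclic (triptyline or imipramine type) antidepressants | Excluded, no exception | Excluded, no exception | Waivable |
| Planned sedation | Excluded, no exception | Not mentioned | Waivable |

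For the drug classes, 7.4 conflicts with two sections. For sedation, it conflicts with 5.2 only.

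**Step 2. Could 7.4 be a separate rule on concomitant medication?** Its wording does not support that reading. It speaks of exclusion from the study, and it includes patients for whom sedation is planned, which is known before treatment. The study anesthetic is given at a single treatment visit. Section 7.4 is in effect criterion 5 restated with an exception added.

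**Step 3. What a waiver would permit, by class**

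- *Ergot-type oxytocics.* Section 2.4.1 says that bupivacaine with epinephrine or other vasopressors "should not be used concomitantly with ergot-type oxytocic drugs, because a severe persistent hypertension may occur". A waiver would allow what 2.4.1 rules out.
- *MAO inhibitors and tricyclics.* Section 2.4.1 says the solution "should be used with extreme caution in patients receiving monoamine oxidase inhibitors (MAOI) or antidepressants of the triptyline or imipramine types", and then chooses exclusion. A waiver contradicts the protocol's own decision, but not a flat prohibition on the drug combination.
- *Sedation.* No hypertension reason is given. The conflict is one of rules only.

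**Step 4. Can a waived patient avoid epinephrine on protocol?** No. Both block solutions contain it, and section 2.2.2 adds: "A supplemental buccal infiltration and intraligamentary (IL) injection will be given with Lidocaine HCl 2% 1:100000 to all patients, irrespective of their grouping". From the concentrations and the cartridge volumes in section 6.1.7:

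- Bupivacaine, 1:200,000 = 5 micrograms/mL. One cartridge: 5 × 1.8 mL = 9 micrograms. Two cartridges: 18 micrograms.
- Lidocaine, 1:100,000 = 10 micrograms/mL. One cartridge: 10 × 1.7 mL = 17 micrograms. Two cartridges: 34 micrograms.
- Ratio per cartridge, lidocaine to bupivacaine: 17 / 9 = 1.89.
- Lidocaine supplement, both arms: a further 10 micrograms per mL. The text does not state its volume, so no total can be given.

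Exposure therefore occurs in both arms and, for the block, is larger in the control arm. Because treatment is randomized and blinded, an approving investigator cannot choose the block with less epinephrine. These figures describe dose and do not estimate risk.

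**The case against.** The strongest reply is that this is a drafting slip with no practical route to harm. Enrolment requires every eligibility criterion to be met, eligibility is verified again at baseline, and neither step offers a waiver, so the clause matters only if staff prefer it to a rule stated elsewhere without exception. Lidocaine with 1:100,000 epinephrine is also the clinic's routine anesthetic, so a waived patient might receive the same drug off study, and less epinephrine from the block if allocated bupivacaine. The outright prohibition applies only to ergot-type oxytocics, which criterion 5 limits to use for uterine contraction; with pregnant patients excluded separately, such candidates are probably rare. For MAO inhibitors and tricyclics, individual clinical review could satisfy a requirement for caution. Section 8.6 places safety oversight with the investigators, and section 2.4.1 provides for monitoring and resuscitation.

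Much of this stands as a limit on size. The documents do not show added risk over off-study care, and few patients are likely to be involved. It does not remove the contradiction. An eligibility rule that staff must disregard for the protocol to work should not stay in the protocol, and 7.4 followed as written permits a combination that 2.4.1 says should not be used.

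Two smaller points are fair. The wording of the drug lists differs slightly (7.4 says tricyclic where the other sections name triptyline and imipramine types, and it omits the uterine-contraction qualifier), though in practice the lists are equivalent. Section 5.8.1, which covers an exclusion criterion discovered after enrolment, permits termination and does not require it.

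**Conclusion.** The concern holds. Section 7.4 makes waivable, without a criterion, an exclusion that section 5.2 states absolutely for all four groups and section 2.4.1 states absolutely for the three drug classes. No other section supplies a rule for the waiver. It should be corrected, as a matter of patient safety and consistent eligibility decisions.

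The number of affected patients is not given, and the effect on the efficacy comparison is expected to be negligible. The consequence is most serious for ergot-type oxytocics, less so for MAO inhibitors and tricyclics, and purely one of consistency for sedation. The conclusion rests on reading the closing exclusion sentence in 2.4.1 as covering all three classes named just before it, which is its natural sense.

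**What to change.** In section 7.4, delete the exception from *unless* to the end of the sentence, and change *should be excluded* to *will be excluded*. Sections 5.2 and 2.4.1 need no change. A cross-reference from 7.4 to criterion 5 would also remove the small differences in drug wording.

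Patients found after enrolment to be using one of these drugs are still provided for, since section 5.8.1 allows the investigator to end their participation.

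The cost is one clause and one verb, with IRB approval of the amendment under section 13.2, and the loss of case-by-case discretion for a few MAO inhibitor, tricyclic or sedation patients. If the sponsor wants to keep that discretion, the alternative is to write the exception, with explicit criteria, into 5.2 and, for the drug classes, into 2.4.1. For ergot-type oxytocics this would run against the hazard statement already in 2.4.1, so deletion is the simpler and safer choice.

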7.5 Prophylactic Medications, Treatments, and Procedures

No prophylactic medications, treatments and procedures are planned for the study unless the subject needs any of those prophylaxis for his/her treatment predetermined by the primary care physician.

7.6 Rescue Medications, Treatments, and Procedures

Subjects will be provided instructions verbally and written regarding rescue medication of ibuprofen and/or acetaminophen. They will be instructed that they can use 400-600 mg ibuprofen and 500 mg acetaminophen every 6 hours if there is no medical contradiction for the use of these medications. These are the routine instructions given after every endodontic treatment. In order to make it standardized, the instructions will be given verbally and written. They will record their analgesic use on the questions that they will receive. If these medications also don't help they will be instructed to call the phone number of the PI and after the phone call, if it is found out necessary, an unscheduled dental visit will be scheduled for the next available time in the clinic, with the treating PG student or they subject will be seen by another available post graduate student, both of whom work under the supervision of NYS Dental Licensed Co-Investigators, on emergency as soon as possible.

8 Assessment of Safety

8.1 Specification of Safety Parameters

The agents used in this study are FDA approved, commercially available products. Therefore, safety parameters are not the main endpoints. If any adverse events (AE), serious adverse events (SAE) or any unanticipated problems (UP) occur, they will be recorded and reported for the protection of human subjects.

CONFIDENTIAL

8.1.1 Definition of Adverse Events (AE)

An **adverse event** (AE) is any symptom, sign, illness or experience that develops or worsens in severity during the course of the study. The adverse events for the study and control agent can be found on the attachment of the agents' package insert. Abnormal results of diagnostic procedures are considered to be adverse events if the abnormality:

- results in study withdrawal
- is associated with a serious adverse event
- is associated with clinical signs or symptoms
- leads to additional treatment or to further diagnostic tests
- is considered by the investigator to be of clinical significance

